Assessments will be conducted at intake, every 4 weeks during the 24-week intervention period, and at a 12-week follow-up period. Participants will be paid \$50 for completing each of the assessments. These assessments may be collected using Qualtrics or REDCap.

Intake Only Assessment Instruments

DSM-5 Checklist for Opioid Use Disorder. The DSM-5 checklist for opioid use disorder is a structured assessment that will be used to determine if participants have opioid use disorder.

Treatment Facilitators and Barriers Questionnaire. This questionnaire will assess participants' self-reported barriers and facilitators to accessing opioid use disorder treatment.

Intake and Major Assessment Instruments

Urine toxicology testing. Urine samples will be collected under observation and tested for opioids and other drugs.

Smartphone Form. This questionnaire will document participants' access to and willingness to use a smartphone during the study.

Time-line follow-back (TLFB). Participants will be asked whether or not they are in treatment for their opioid use disorder, including treatment other than buprenorphine (e.g., methadone maintenance). For participants who report being in buprenorphine treatment, the TLFB procedure will be used to elicit participants' self-reported taking of their buprenorphine dose each day. Pharmacy and/or clinic records (with participant permission) may be used to confirm self-reported data.

Opioid Overdose Risk Assessment. An opioid overdose risk assessment will be used to assess the rate at which participants report engaging in behaviors that may put them at risk for an opioid overdose.

The Addiction Severity Index – Lite (ASI-Lite). The ASI-Lite is a structured interview designed to assess problem severity in areas commonly affected by drug and alcohol use (medical, legal, employment, family/social, and psychiatric) with good reliability and validity.

The Beck Depression Inventory (BDI). The BDI is a 21-item questionnaire designed to screen for severity of depression.

Treatment Acceptability Questionnaire. To assess the acceptability of our intervention, we will administer a Treatment Acceptability Questionnaire to participants who are exposed to our smartphone incentive intervention at the end of the 24-week intervention period.

- b. Study duration and number of study visits required of research participants.

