- a. Primary outcome variable.

Study 1 and Study 2 have the same primary outcome:

Specific aim. *Assess efficacy of Video DOT+ in promoting buprenorphine treatment adherence as assessed by urine drug screens.* We will assess the percentage of participants with buprenorphine-positive urine samples at the 4-week assessments during the 24-week intervention evaluation period (Yes/No at each assessment). Hypothesis: We expect that Video DOT+ participants will have more buprenorphine-positive urine samples during the 24-week intervention relative to the Usual Care Control participants.

- b. Secondary outcome variables.

Study 1 and Study 2 have the same secondary outcomes:

Specific aim. *Assess efficacy of Video DOT+ in promoting self-reported buprenorphine treatment*

Date: February 11, 2020

Principal Investigator: [name]

Application Number: IRB00186156

adherence. We will assess the number of days participants report taking their daily buprenorphine dose during the 30 days prior to each of the 4-week assessments during the 24-week intervention evaluation period (based on TLFB). *Hypothesis:* We expect that Video DOT+ participants will have more days of taking their buprenorphine dose as prescribed during the 24-week intervention relative to the Usual Care Control participants.

Specific aim. Assess efficacy of Video DOT+ in promoting linkage to buprenorphine treatment. We will assess the percentage of participants who link to buprenorphine treatment during the 24-week intervention evaluation period (Yes/No, based on self-report and medical records). *Hypothesis:* We expect that more Video DOT+ participants will link to buprenorphine treatment during the 24-week intervention relative to the Usual Care Control participants.

Specific aim. Assess efficacy of Video DOT+ in promoting retention in buprenorphine treatment. We will assess the total number of days participants are in buprenorphine treatment from the time of randomization until the last day of medication during the 24-week intervention evaluation period (based on self-report and medical records). *Hypothesis:* We expect that Video DOT+ participants will be retained in buprenorphine treatment for more days during the 24-week intervention relative to the Usual Care Control participants.

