Specific aim. Assess efficacy of Video DOT+ in reducing opioid use. We will assess the percentage of participants with opioid-positive urine samples (excluding buprenorphine and methadone if self-report and medical records confirm that the participant is enrolled in buprenorphine or methadone treatment) at the 4-week assessments during the 24-week intervention evaluation period (Yes/No at each assessment).

Hypothesis: We expect that Video DOT+ participants will have fewer opioid-positive urine samples during the 24-week intervention relative to the Usual Care Control participants.

Specific aim. Assess efficacy of Video DOT+ in reducing risk of opioid overdose. We will assess the rates at which participants report engaging in overdose risk behaviors at the 4-week assessments during the 24-week intervention evaluation period (based on total scores from the opioid overdose risk assessment).

Hypothesis: We expect that Video DOT+ participants will engage in lower rates of opioid overdose risk behaviors during the 24-week intervention relative to Usual Care Control.

Specific aim. Assess efficacy of Video DOT+ in promoting buprenorphine treatment engagement and adherence, and reducing opioid use and risk of opioid overdose after the intervention ends. We will assess these outcomes at the 12-week follow-up after the intervention ends. *Hypothesis:* We expect that Video DOT+ participants will have better buprenorphine treatment outcomes relative to the Usual Care Control participants after the intervention ends.

c. Statistical plan including sample size justification and interim data analysis.

Statistical Analyses

Separate statistical analyses will be conducted for Study 1 and Study 2, using the procedures described below.

We will analyze measures assessed repeatedly over time with a longitudinal logistic regression model. Within-person correlated outcomes will be handled using generalized estimating equations (GEE; Zeger, Liang, & Albert, 1988). Measures assessed once will be analyzed using logistic regression. The magnitude of effects will be expressed using odds ratios with 95% confidence intervals. Retention in buprenorphine treatment during the 24 weeks of the intervention period will be analyzed with a Cox proportional hazards model. We will adjust the intent-to-treat analyses for covariates used for stratification (Pocock, Assmann, Enos, & Kasten, 2002). Tests will be two-sided and, because we have one primary outcome, alpha will be set at 0.05.

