Primary outcome analyses. The primary outcome measure will be the percentage of participants with buprenorphine-positive urine samples at the 4-week assessments during the 24-week intervention

Date: February 11, 2020

Principal Investigator: [name]

Application Number: IRB00186156

[figure not shown]
evaluation period (Y/N at each assessment). We will fit a longitudinal logistic regression model $\text{logit}(Y_{ij}) = \beta_0 + \beta_1 tx + \beta_2 \cdot 3x_{2-3} + \varepsilon_{ij}$, where Y_{ij} is evidence of buprenorphine adherence for the i th person at the j th timepoint (6 visits over 24 weeks), β_1 is the covariate of interest representing the expected increase in log odds of evidence of buprenorphine adherence as a function of assignment to the treatment group, and β_2 are the coefficients for the 2 randomization covariates. We will fit models with time and time by treatment interactions secondarily. These models will allow us to look at change over time in buprenorphine adherence in each study arm.

Secondary outcome analyses. We will fit longitudinal logistic regression models, similar to those described for the primary outcome measure, for self-reported buprenorphine treatment adherence, opioid use, and opioid overdose risk behaviors. Linkage to buprenorphine treatment and post-intervention effects will be assessed by logistic regression. Retention in buprenorphine treatment during the 24 weeks of the intervention period will be analyzed with a Cox proportional hazards model.

Missing data. We expect to collect $\geq 85\%$ of the study assessments. Our primary approach to handle missing data will be to impute missing values as the adverse outcome (e.g., buprenorphine-negative urine sample). Model parameter estimates from this approach will be compared to a method without imputation. If these methods yield differing results, conclusions will need to be tentative, but results from both approaches will be reported in publications. To investigate sensitivity to missing values, participants with and without missing values will be compared by covariates and group assignment. If rates are higher than expected, we may use mixed effects models rather than GEE estimation, as the former has less strict assumptions regarding missing data (missing at random, rather than missing completely at random). If the data are missing not at random, then we will fit pattern mixture models as described by Hedeker and Gibbons (1997).

Power Analyses

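### The overdose-risk total score is assigned a logistic model modelled on a Yes/No outcome, with no cut-point or other response form stated; the self-reported day count also lacks a stated form

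*Combined protocol and SAP*

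**What the plan says.** Section 7b sets the scale of each secondary outcome. Opioid use is a Yes/No urine result at each assessment, and linkage is "Yes/No, based on self-report and medical records". Two outcomes are different in kind. Self-reported adherence is "the number of days participants report taking their daily buprenorphine dose during the 30 days prior to each of the 4-week assessments", and overdose risk is "based on total scores from the opioid overdose risk assessment".

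Section 7c assigns logistic regression to every outcome except retention, with odds ratios as the effect measure. For the repeated secondary outcomes it plans "longitudinal logistic regression models, similar to those described for the primary outcome measure, for self-reported buprenorphine treatment adherence, opioid use, and opioid overdose risk behaviors". The 12-week post-intervention outcomes also go to logistic regression. The missing-data paragraph makes imputation of the adverse outcome the primary approach, gives a urine result as its only example, and adds a comparison without imputation.

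Two points in section 4 bear on this. The overdose-risk instrument is listed under "Intake and Major Assessment Instruments", so a baseline score exists. On the follow-back, everyone is asked whether they are in treatment, and then: "For participants who report being in buprenorphine treatment, the TLFB procedure will be used".

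**The concern.** The primary model takes a 0/1 response. A total score is not a 0/1 response, and the plan names no threshold, no maximum to scale by and no ordinal form. An analyst who follows the primary model literally has to choose a cut. That loses information, and in a trial where participants are unblinded (section 4c) it leaves a consequential choice open until after data are seen. The missing-data rule has the same gap, because no adverse value is defined for a score.

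For the day count, a logistic model can be right if the response is days out of 30, but the plan does not say that this is what it means. Nor does it state the value for someone assessed who is not in treatment. The hypothesis speaks of "more days of taking their buprenorphine dose as prescribed", which fits a person with a prescription and is silent on one without. If such people were coded as missing, the comparison without imputation would drop them.

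**Working it through.** **The plan's own figures.** The plan gives no effect size, power, score range or SD for these two outcomes, so there is nothing to reproduce. The 64 participants in section 7c relate to the primary outcome and are not in dispute. Below, 64 is taken as 32 per arm (1:1 allocation assumed).

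**Outcome against model**
- Primary urine result: Yes/No, logistic. Fits.
- Opioid use: Yes/No, logistic. Fits.
- Linkage: Yes/No, logistic. Fits.
- Self-reported adherence: days in 30, logistic. Fits only as a binomial proportion, which is not stated.
- Overdose risk: "An opioid overdose risk assessment will be used to assess the rate at which participants report engaging in behaviors", summarised as a total score, logistic. Does not fit without a cut or a recoding, and neither is stated.

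**Score at a single time point (the 12-week follow-up), normal score assumed, no missing data.** A cut with a share q above it keeps phi(z)^2 / [q(1-q)] of the information, where z is the normal quantile at the cut and phi is the normal density.
- Median: 0.3989^2 / 0.25 = 0.64
- 70/30: 0.3477^2 / 0.21 = 0.58
- 80/20: 0.2800^2 / 0.16 = 0.49
- 90/10: 0.1755^2 / 0.09 = 0.34

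In terms of 64 participants, a median split is worth 64 x 0.637 = 41 and a 90/10 cut 64 x 0.342 = 22.

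**Score over six visits.** With exchangeable correlation of 0.3 to 0.7 the loss is smaller: a median split keeps 0.81 to 0.84, and a 90/10 cut 0.51 to 0.53.

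**Power by simulation.** 32 per arm, six visits, 15% missing, correlation 0.5, effect 0.40 SD, independence GEE with robust SEs. Ranges are given where runs differed.

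| Analysis | Score | Median split |
|---|---|---|
| No imputation, without intake score | 55-56% | 45-48% |
| No imputation, with intake score | 78% | 61-64% |
| Worst score at 2.5 SD, without intake score | 43-46% | 43-45% |
| Worst score at 2.5 SD, with intake score | 57% | 55-59% |

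Why the gain disappears under imputation: at one time point, with 15% imputed k SD above the mean, a linear model keeps 0.85^2 / (0.85 + 0.1275 k^2). At k = 2.5 this is 0.7225 / 1.647 = 0.44. A median split keeps (0.85 x 0.3989)^2 / (0.575 x 0.425) = 0.47. The extreme imputed values inflate the variance of the linear model but not that of the split. A rank-based analysis with the intake score had 62% power in the simulation.

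**Day count, assumed inputs.** Suppose 30% of control and 55% of Video DOT+ participants are in treatment, and treated people in both arms take 20 of 30 days.
- Untreated counted as zero: 0.30 x 20/30 = 0.200 against 0.55 x 20/30 = 0.367. OR = (0.367/0.633) / (0.200/0.800) = 2.32.
- Untreated dropped: 0.667 in both arms. OR = 1.00.

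With 24 days (control) against 22 (Video DOT+), the same steps give 2.14 and 0.69. The rule can therefore matter, but it need not. In a simulated mixed scenario (linkage 42% against 60%, mean dosing 0.65 against 0.80) the two rules gave OR 2.32 against 2.19 and the same rejection rate, 54%.

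**The case against.** The strongest reply on the score is that similarity to the primary model does not mean a binary response. A cumulative-logit model is also a logistic model, yields an odds ratio and needs no cut; so would scaling by the instrument's maximum. That stands: a reader might infer that the plan has chosen to dichotomise, and the documents do not say so. What remains is that the only model written out is binary and no alternative form is given.

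A reader might also set the score with intake adjustment (78%) against a median split without it (47% in one run) and blame the cut for all 31 points. About 78 - 55 = 23 of those come from the intake covariate, which the plan does not currently include, and about 55 - 47 = 8 from not cutting. Under the plan's primary missing-data rule, a linear model gains almost nothing over a median split.

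On the day count, a reader might infer that the plan analyses treated people only. The text points the other way. Section 4 asks all participants their treatment status, section 7b defines the outcome over participants, section 7c calls the analyses intent-to-treat, and the primary imputation rule would give zero days. Someone assessed who answers no has an observed status. The treated-only result arises only if that answer is coded as missing and the comparison without imputation is then used. Nor is a cut on days always weaker: at 24 or more days it rejected more often than days out of 30 in two of three simulated scenarios (97% against 72%, and 63% against 53%). The case for days out of 30 is that it matches the stated outcome.

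**Conclusion.** The point holds as a gap in specification with a modest analytic cost. The overdose-risk score is assigned a model that does not fit it without an unplanned cut or recoding, at the six visits and at 12 weeks, and its adverse value is undefined. For self-reported adherence the logistic family is suitable; only the response form and an explicit zero-day statement are lacking.

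Like for like and without imputation, a median split costs roughly 7 to 11 points of power without the intake score (55-56% against 45-48%) and 14 to 17 with it (78% against 61-64%). The cost is close to nil under worst-score imputation. A cut further from the median loses more information. All of this assumes a normal score and chosen values for effect, correlation and missingness; the documents give no range or SD, so the figures show that the choice can matter, not by how much here.

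Severity is minor. Both outcomes are secondary, in pilot studies, and neither the primary analysis nor its sample size depends on them.

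**What to change.** Amend section 7c before outcome data are seen.

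1. Analyse the overdose-risk total score as a score, at the six visits and at the 12-week follow-up, with one form fixed in advance. Use GEE with identity link and robust SEs (mean difference, 95% CI), or a cumulative-logit model (odds ratio) if the instrument has few levels by design. Let the design of the instrument decide, not the observed data. Adjust for arm, sex, cocaine status and the intake score.
2. Define the adverse value for a missing score and report the analysis without imputation beside it, since worst-score imputation removes most of the gain from not cutting in a linear model. Keep the mixed-model fallback already planned.
3. Analyse self-reported adherence as days out of 30 with a binomial logit GEE and robust SEs. State that assessed participants with no buprenorphine treatment in the window are observed zeros in both the imputed and unimputed analyses.
4. Keep logistic models for the true Yes/No outcomes.

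The cost is a few sentences of SAP text and some code. The intake score is already collected and no new instrument is needed. If staff now take the follow-back only from people currently in treatment, it should also cover anyone treated earlier in the window. The one drawback is that, with the identity link, a mean difference replaces the planned odds ratio for one secondary outcome.

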Participants will be randomly assigned to a Usual Care Control or Video DOT+ group. A computerized urn randomization procedure (Wei & Lachin, 1988) will be used to randomize participants and to balance groups on two baseline characteristics that may influence outcome: (1) sex (male/female) and (2) intake urine sample positive for cocaine (Yes/No). Participants will be stratified based on sex and evidence of cocaine use because each has been associated with buprenorphine treatment outcomes (Marsch et al., 2005; Sullivan et al., 2010). While it might be desirable to stratify on other variables, increasing the number of variables is not practical given the sample size proposed for this study.

STUDY 2

Computer-Based Education Program

Upon enrollment in Study 2, participants will be taught how to use the Video DOT application through a computer-based education program. All participants who are eligible for Study 2 will be invited to complete the computer-based program. After participants complete the computer-based program, they will be invited to participate in a 7-day smartphone induction period (as described in detail below).

Course Content. The content of the computer-based program was developed using screenshots of the different sections of the study smartphone app. The program teaches participants the main functions of each setting in the app while using the screenshots as a visual aid.

Computer-Based Education Program. The course is divided into Modules consisting of Presentation and Mastery Units. Presentation Units were designed to introduce new material, while Mastery Units allow participants to practice answering questions about that material. Each Mastery Unit consists of a series of question screens with questions about the content in the previous Presentation Unit. Question

Date: February 11, 2020

Principal Investigator: [name]

Application Number: IRB00186156

screens may be presented in random order in a one-minute practice trial (i.e., “timing”). Participants will be able to earn \$30 for completing the computer-based education program.

Smartphone Induction

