Study participation for Study 1 and Study 2 will include a 24-week intervention evaluation period and a 12-week follow-up period for a total study duration of 36 weeks. Outcome assessments will be conducted at intake, every 4 weeks during the 24-week intervention period, and at a 12-week follow-up period.

Date: February 11, 2020

Principal Investigator: [name]

Application Number: IRB00186156

c. Blinding, including justification for blinding or not blinding the trial, if applicable.

Participants in Study 1 and Study 2 will not be blinded as to their study condition because participants in the incentive intervention cannot be blind to that intervention.

d. Justification of why participants will not receive routine care or will have current therapy stopped.

N/A

e. Justification for inclusion of a placebo or non-treatment group.

N/A

f. Definition of treatment failure or participant removal criteria.

Participants will be removed from either study if they threaten the safety of staff or other research participants, or of any other persons on the Johns Hopkins Bayview Campus.

g. Description of what happens to participants receiving therapy when study ends or if a participant's participation in the study ends prematurely.

Throughout Study 1 and Study 2, participants will be given referrals to services they might need (e.g., drug counseling, housing, medical, or employment services). Participants will continue to receive buprenorphine treatment as long as that treatment is available in the program they attend.

5. Inclusion/Exclusion Criteria

Study 1

Applicants will be invited to participate in this study if they: a) are \geq 18 years old, b) meet DSM-5 criteria for current opioid use disorder, c) provide an opioid-positive urine sample, d) report not receiving any type of drug abuse treatment in the past 30 days, and e) are interested in receiving buprenorphine treatment. Applicants will be excluded if they: a) have current suicidal/homicidal ideation, b) are pregnant or nursing, or c) are unwilling or unable to use a smartphone.

Study 2

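### The overdose-risk models leave out the intake overdose-risk score, a baseline value already scheduled for collection that could add precision at almost no cost

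*Combined protocol and SAP*

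**What the plan says.** Reducing overdose risk is a secondary aim of both studies. Section 7b defines the outcome at the 4-week assessments as "based on total scores from the opioid overdose risk assessment".

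The instrument appears in section 4a under the heading "Intake and Major Assessment Instruments", where the text reads "An opioid overdose risk assessment will be used to assess the rate at which participants report engaging in behaviors". The schedule in the same section is "Assessments will be conducted at intake, every 4 weeks during the 24-week intervention period, and at a 12-week follow-up period". An intake score is therefore planned for everyone. Intake comes before randomization, because the intake cocaine result feeds the urn procedure.

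Section 7c gives the general adjustment rule: "We will adjust the intent-to-treat analyses for covariates used for stratification". Those covariates are sex and a cocaine-positive intake urine, the same two in Study 1 and Study 2. The primary model contains treatment and these two terms, fitted to six post-randomization visits. The paragraph on secondary outcomes then applies models "similar to those described for the primary outcome measure, for self-reported buprenorphine treatment adherence, opioid use, and opioid overdose risk behaviors". Post-intervention effects at the 12-week follow-up are assigned to logistic regression. The intake overdose-risk score is not entered in any model, and the randomization does not balance on it.

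**The concern.** The intake value of an outcome is often a good predictor of its later values. When it is left out, stable differences between participants in risk behaviour stay in the comparison as noise. A chance difference between arms at entry also carries over, in part, to the estimated effect. Both matter more in small samples, and section 7 says that the two studies are analysed separately.

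The point is specific to this outcome. Eligibility requires each applicant to "c) provide an opioid-positive urine sample" and to report no drug abuse treatment in the past 30 days, so intake values for opioid urine, linkage and retention can hardly differ between participants. No criterion restricts the overdose-risk score.

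At stake is the precision of one stated secondary aim, in return for a single sentence in the plan.

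**Working it through.** **Inputs from the documents.** Six visits over 24 weeks, two-sided alpha 0.05, and 64 to be randomized (section 7c, Power Analyses). The 64 is for the primary outcome; no power figure is given for overdose risk. The opening summary gives N = 105 without stating the split between the studies.

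**Assumed inputs.** Within-person correlation between visits (rho), and the correlation r of the intake score with each follow-up score, read as what remains after sex and cocaine. The documents give neither.

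**The plan's own figure.** With exchangeable correlation, n per arm = (1.96 + 0.842)² × [p1(1−p1) + p2(1−p2)] × (1 + 5·rho) / (6 × 0.25²). For an assumed control rate of 25%, an intervention rate of 50% and rho = 0.5: 7.85 × 0.4375 × 3.5 / 0.375 ≈ 32 per arm, or 64 in total. The 64 is plausible, but it cannot be confirmed because the control rate and rho are not in the available text. It does suggest rho = 0.5 as a reasonable working value.

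**Effect of adding the intake score (score treated as numeric, mean of six visits).**
- Variance of the six-visit mean, in units of the single-visit variance: V = (1 + 5 × 0.5)/6 = 0.583.
- Share explained by the intake score: R² = r²/V.
- Equivalent sample size: 64/(1 − R²).
- Power, for an effect with 80% power without the score: Φ(2.802/√(1 − R²) − 1.96).

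| r | R² | Equivalent N | Power |
|---|---|---|---|
| 0.1 | 0.017 | 65 | 80.7% |
| 0.2 | 0.069 | 69 | 82.7% |
| 0.3 | 0.154 | 76 | 86.1% |
| 0.5 | 0.429 | 112 | 96.0% |

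At r = 0.3, changing rho to 0.3 gives 88.6%, and changing it to 0.7 gives 84.8%.

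**Chance imbalance at N = 64.** The standard error of the intake difference is √(4/64) = 0.25 SD. A gap above 0.25 SD has probability 32%, and one above 0.5 SD has 4.6%. A gap of 0.5 SD shifts the contrast by r × 0.5: 0.15 SD at r = 0.3 and 0.25 SD at r = 0.5. The standard error of the contrast is √(0.583 × 4/64) = 0.191 SD, so the shifts are about 0.8 and 1.3 standard errors. If the 105 covers both studies, at least one has 52 or fewer; at N = 52 the two probabilities become 37% and 7%.

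**Check on the planned model type.** GEE logistic regression was simulated with a dichotomised score, N = 64 and 300 runs per setting.

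| r, rho | Power without → with score | Null rejection without → with score |
|---|---|---|
| 0.3, 0.5 | 76% → 84% | 4.3% → 6.0% |
| 0.5, 0.5 | 78% → 92% | 8.0% → 9.0% |
| 0.6, 0.6 | 78% → 95% | 8.7% → 9.0% |

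With 300 runs, the simulation error is about √(0.8 × 0.2/300) = 2.3 points near 80% power and √(0.05 × 0.95/300) = 1.3 points near 5%. The direction of the gain is clear; its exact size is not.

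**The case against.** The strongest reply is that this is a preference and not an error. The plan already prespecifies covariate adjustment, randomization protects the comparison, and the outcome is secondary, without a power claim, in pilot studies. That stands. A reader might infer that the overdose-risk comparison is unadjusted, biased or prone to false positives. The documents do not support this: sex and intake cocaine are in the model, the average type I error is not harmed by the omission, and an intake imbalance passes through only in proportion to r.

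A reader might also apply the familiar multiplier 1/(1 − r²) and quote a large saving in participants. That is a linear result for one numeric follow-up. The plan has six visits and a logistic model, in which adding a predictor also moves the odds ratio from marginal towards conditional. The table above is likewise a numeric approximation.

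The size is uncertain too. At r = 0.1 the gain is under one point. Everyone enters opioid-positive and out of treatment, which could narrow the range of intake scores. Coding missing visits as the adverse outcome could dilute r. The documents give no range or distribution for the instrument.

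One defence does not stand. The remark in section 4 that more variables are impractical concerns stratification in the randomization, not terms in the analysis model.

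**Conclusion.** The omission is real, and correcting it is a low-cost improvement; the analysis as written is not invalid. Under the stated assumptions (rho = 0.5, N = 64, numeric score), the gain from 80% power is under 1 point at r = 0.1, about 3 points at r = 0.2, 6 at r = 0.3 and 16 at r = 0.5. A logistic simulation of a dichotomised score agrees in direction. These figures describe the 24-week model only; the gain at the single 12-week follow-up was not quantified.

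The 64 should not be read as a confirmed size for either study, since it is the number required for the primary outcome and the split of the 105 is not stated. The benefit also cannot be pinned down until the plan says how a total score becomes the response in a logistic model, because no cut-off or other form is given.

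**What to change.** In section 7c, for both studies:

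- Prespecify the intake overdose-risk total score as a numeric covariate, alongside sex and intake cocaine, in the 24-week overdose-risk model and in the 12-week follow-up model of the same outcome.
- State the response form used for the total score. Keep the intake score numeric whichever form is chosen.
- Note that the reported odds ratio is then conditional on the intake score, and fix this before outcome data are examined.
- State how a missing intake score is handled, for example by simple mean imputation of the covariate.

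The cost is a few lines of text, one extra model term and a slightly different odds-ratio estimand. No new data are needed.
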